6.4 Method of statistical analysis

6.4.1 Primary outcome variables

The proportion of subjects with healed RE verified at Visits 3 or 4 in the analysis set is defined as the healing rate at Week 8.

The healing rate of RE at Week 8 and its two-sided 95% confidence interval will be calculated for each group. The difference in healing rates between the D40 group and O20 group (D40 group – O20 group) and between the D20 group and O20 group (D20 group – O20 group) along with the two-sided 95% confidence intervals will be obtained. It is concluded that the non-inferiority of D40 to O20 is verified if the lower limit of the two-sided 95% confidence interval of the difference between D40 group and O20 group exceeds -10%. If the non-inferiority of D40 to O20 is verified, the verification of the non-inferiority of D20 to O20 will be investigated similarly.

The healing rate at Week 8 will be compared between D40 group and O20 group and between D20 group and O20 group using Cochran-Mantel-Haenszel test stratified by baseline LA classification or CYP2C19 genotype. In these comparisons, the significant level will not be adjusted.

The healing rate at Week 8 in each subgroup and its two-sided 95% confidence interval will be calculated by dose group regarding the following factors.

- Sex
- Age (<65 years old, ≥65 years old)
- Presence or absence of Hp infection
- CYP2C19 genotype (homo EM, hetero EM, PM)

- Baseline LA classification (grade A/B, grade C/D)

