3.5 Method of assigning subjects to treatment groups

Subjects will be classified based on the LA classification in grade A/B and C/D, and randomised to one of the D20, D40 or O20 groups in the proportion of 1:1:1 in each group. A randomisation list will be prepared by the Subject Registration Centre.

The investigator(s) will explain about the study to potential candidates and obtain written informed consent. At the time of informed consent obtained, an Enrolment code will be allocated to each subject at each study site to identify the subject. The Enrolment code (E00XXYYY) is composed of 4 digits (00XX) of centre number and 3 digits (YYY) of consecutive number in order of registration to screening at each study site. For centre number(s), see [REDACTED]

Prior to randomisation, the investigator(s) will judge eligibility of the subjects who provided informed consent. After confirming the eligibility of the subject who has given his/her consent, the investigator(s) will enter necessary information in the subject registration form and send it to the Subject Registration Centre by facsimile.

The Subject Registration Centre will check the eligibility of the subject and register the subject. The Subject Registration Centre will allocate a Randomisation code to the subject and send the registration confirmation form containing Randomisation code to the investigator(s) and AstraZeneca KK by facsimile.

After obtaining the registration confirmation form from the Subject Registration Centre, the investigator(s) will start administration of the investigational product to the registered subject following the randomisation code written in the registration confirmation form.

[figure not shown]
The investigator(s) will keep the registration confirmation form sent from the Subject Registration Centre in the investigator's study file (see Section 7.6.5.1).

Information on the Subject Registration Centre is given below.

[Subject Registration Centre] [REDACTED] [REDACTED] [REDACTED] [REDACTED]

The flowchart for subject registration and prescription of the investigational product is shown in [Figure 2](#).

Figure 2 Flow chart for subject registration and prescription of the investigational product

If a subject discontinues from the study, the enrolment code of the subject will not be reused, and the subject will not be allowed to re-enter the study.

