6.5 Determination of sample size

There are two criteria that are used to determine the sample size for this study.

One is the statistical power to show the non-inferiority of D20 to O20 in healing of RE at Week 8. The other is the probability of obtaining that the observed healing rate of D20 is lower than that of O20 under an assumption that the true healing rate of D20 is higher than that of O20.

The non-inferiority will be concluded when the lower limit of two-sided 95% confidence interval of the difference of healing rates at Week 8 between D20 and O20 is higher than or equal to -10%. Based on the results of the overseas studies (SH-QBE-0013/172, SH-QBE-0016/173, SH-QBE-0017/174, SH-QBE-0052/222), 172 patients per treatment group are required to keep a 90% power or more with the lower limit of two-sided 95% confidence interval of the difference to be greater than or equal to -10% under the assumption that the healing rates of RE at Week 8 are 85% for D20 and 82% for O20, respectively.

In order to ensure sufficient “power” for the observed responses to show that the healing rate of D20 is numerically higher than that of O20, it is calculated that 182 patients will be needed for each of these treatment groups to ensure a less than 20% probability that the healing rate of D20 would result in an observed response rate greater than that for O20.

Accordingly, we decided to randomize 185 patients per group in the planned study to fulfil the above two criteria (a total of 555 patients in 3 groups).

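### Randomisation is stratified by LA grade, but the interval that decides non-inferiority reads as unstratified; it is valid but somewhat conservative if grade is prognostic, and stratifying it is a free improvement

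*Protocol*

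**What the plan says.** Randomisation (Protocol 3.1 and 3.5) is 1:1:1 within two strata: "Subjects will be classified based on the LA classification in grade A/B and C/D, and randomised" to the three groups. Section 3.5 also manages accrual by stratum, with at least 100 C/D patients and A/B allocation closed at 455.

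The primary rate, that for Week 8 (Protocol 6.4.1), is defined over everyone: "The proportion of subjects with healed RE verified at Visits 3 or 4 in the analysis set is defined as the healing rate at Week". Next comes the decision rule: D40 is non-inferior if "the lower limit of the two-sided 95% confidence interval of the difference between D40 group and O20 group exceeds -10" per cent. D20 is examined in the same way only if D40 passes.

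Stratification enters 6.4.1 one paragraph later, where healing rates are compared "using Cochran-Mantel-Haenszel test stratified by baseline LA classification or CYP2C19 genotype". Healing rates by LA subgroup are also planned for each group. Neither of these decides non-inferiority.

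The sample size (Protocol 6.5) assumes "healing rates of RE at Week 8 are 85% for D20 and 82% for O20, respectively", and states that "172 patients per treatment group are required to keep a 90% power or more". The number randomised is 185 per group.

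**The concern.** When randomisation is balanced within a prognostic factor, chance imbalance on that factor no longer adds to the variance of the treatment difference. A crude binomial variance still counts it, so the interval is too wide and over-covers. LA grade is a plausible prognostic factor: section 3.2.1 describes A/B as mild and C/D as severe, and reports that the dose groups differed in healing only in C/D.

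What is at stake is efficiency. Both non-inferiority conclusions rest on this type of interval. Testing is sequential, so a miss on D40 also closes D20. Section 6.4.2.1 analyses Week 4 in the same way as the primary variable, so the choice carries over. Precision matters most when the true difference is near zero, where power is lowest.

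**Working it through.** **Inputs from the protocol.** Margin 10 points and two-sided 95% interval (6.4.1); 85% versus 82%, 172 required and 185 randomised per group (6.5); A/B cap 455 and C/D minimum 100 (3.5), giving a C/D share w = 100/555 = 0.180.

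**Assumptions.** The healing gap g between A/B and C/D is not in the protocol, so it is varied from 10 to 35 points. The treatment difference is taken as the same in both strata.

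**Step 1: reproduce the plan's figure.** With the unstratified variance:
- v = 0.85×0.15 + 0.82×0.18 = 0.2751
- n = v(1.960 + 1.282)²/(0.03 + 0.10)² = 171.04, rounded up to 172. This matches the protocol.
- Power = Φ(0.13/√(v/n) − 1.960), which is 90.2% at n = 172 and 92.1% at n = 185.

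The sample size was therefore derived for a crude difference, and the plan meets its 90% target on that basis.

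**Step 2: variance saved by stratifying.** With overall rate p, the stratum rates are p + wg (A/B) and p − (1−w)g (C/D). Per arm, the within-stratum variance is p(1−p) − w(1−w)g², so the proportional saving is w(1−w)g²/[p(1−p)]. At p = 0.82, w(1−w) = 0.1477 and p(1−p) = 0.1476, so the saving is close to g²: 1.0%, 4.0%, 9.0% and 12.3% for gaps of 10, 20, 30 and 35 points.

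**Step 3: power and coverage, normal approximation.** Let SE_c be the crude and SE_s the stratified standard error, and d the true difference.
- Crude interval under stratified randomisation: power = Φ((0.10 + d − 1.960·SE_c)/SE_s)
- Stratified interval: power = Φ((0.10 + d)/SE_s − 1.960)
- Coverage of the crude interval = 2Φ(1.960·SE_c/SE_s) − 1

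Example, g = 0.30 and d = 0: SE_c = √(2×0.1476/185) = 0.03995 and SE_s = 0.03995×√0.910 = 0.03810. Power goes from Φ(0.570) = 71.6% to Φ(0.664) = 74.7%, and crude coverage is 96.0%.

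| Gap (points) | Variance saved | Power at +3, crude → stratified | Power at 0, crude → stratified | Crude coverage at 0 |
|---|---|---|---|---|
| 10 | 1% | 92.2 → 92.4% | 70.8 → 71.1% | 95.1% |
| 20 | 4% | 92.5 → 93.1% | 71.0 → 72.4% | 95.5% |
| 30 | 9% | 93.1 → 94.4% | 71.6 → 74.7% | 96.0% |
| 35 | 12% | 93.5 → 95.1% | 71.9 → 76.2% | 96.4% |

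The saving in the table is at 82% in both arms. At 85% versus 82% it is 1, 4, 10 and 13%.

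**Step 4: simulation check** (152 A/B and 33 C/D per arm, Wald intervals). Power gains were about 0.2, 0.7, 1.3 and 1.7 points at +3, and about 0.5, 1.5, 3.4 and 4.5 points at zero. Crude coverage at zero was about 95.0, 95.5, 95.9 and 96.3%. These agree with the approximation to within a few tenths of a point.

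**Step 5: type I error at the −10 point margin** (simulated, one-sided, gaps of 10, 20, 30 and 40 points). The crude interval gives 2.5, 2.3, 2.1 and 1.8%; the stratified Wald interval gives about 2.6% throughout.

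**Sensitivity to the C/D share.** 18% follows from the planned minimum of 100. At a 30% share the gains at +3 are 0.2, 0.8, 1.7 and 2.1 points for the same four gaps.

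**The case against.** The strongest reply has four parts.

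- **The premise is inferred.** Section 6.4.1 never calls the interval unstratified and names no method, and section 6.1 promises a comprehensive statistical analysis plan before unblinding. A reader might infer that the protocol prescribes a crude Wald interval; it does not say so. The inference rests on the whole-set definition of the rate, on stratification being named for the test but not for the interval, and on the exact match of 172. Together these make the crude reading the natural one, but the unseen analysis plan may settle it otherwise.
- **Nothing is invalid.** A reader might infer that a non-inferiority claim is put at risk. It is not: the crude interval errs on the conservative side. This stands in full.
- **No planned power is lost.** A reader might infer an underpowered trial. The 172 was computed for the crude difference and 185 gives about 92%, so the loss is only relative to a more efficient analysis. This also stands.
- **The gain may be small.** For gaps of 20 points or less it is below 1 point at +3 and about 1.5 points at zero. Gains of 3 points or more at zero need a gap of about 30 points, which the protocol neither supports nor excludes. Part of the simulated gain also reflects the slightly liberal stratified Wald interval; the score-type intervals recommended below were not simulated.

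It might also be said that the stratified test and the crude interval contradict each other. They do not: one compares healing rates between groups, the other addresses the margin. The mismatch is untidy, not an inconsistency.

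None of this is a reason to leave the randomisation factor out of the deciding interval, since including it costs nothing.

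**Conclusion.** The point holds as an efficiency and consistency improvement, not as an error of validity. On its natural reading, the deciding interval ignores the factor on which randomisation is stratified. If LA grade is prognostic, the interval over-covers modestly and forgoes between about 0.2 and 1.7 points of power at the planning difference, and between about 0.5 and 4.5 points if the drugs are equal.

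These ranges rest on assumed A/B minus C/D healing gaps of 10 to 35 points, an 18% C/D share, 185 evaluable patients per arm, O20 healing at 82% and a common treatment difference across strata. The last may not hold for D40: section 3.2.1 reports that the 40 mg group healed more often in C/D but not in A/B. That is why the stratum weights should be fixed in advance.

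**What to change.** State in 6.4.1, and carry into the analysis plan before unblinding, that:

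- the -10% rule is applied to the risk difference stratified by the randomisation factor (LA A/B, C/D), for D40 and then D20;
- the weights are fixed in advance, either Mantel-Haenszel or stratum-size;
- the two-sided 95% interval is a stratified score-type interval (stratified Miettinen-Nurminen or Newcombe), not stratified Wald, which runs slightly liberal at about 2.6% one-sided;
- the within-stratum differences are reported with 95% intervals, and the crude interval is kept as supportive.

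The cost is a short addition to the text and some extra programming. It needs no additional patients, data or change to the sample size.

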6.4.2 Secondary outcome variables

In the analyses for the secondary outcome variables, only FAS will be used for the efficacy variables and the safety analysis set will be used for all safety variables.

6.4.2.1 Efficacy

Presence/absence of RE at Week 4 according to the LA classification

The proportion of subjects with healed RE verified at Visit 3 in the analysis set is defined as the healing rate at Week 4.

The healing rate of RE at Week 4 and its two-sided 95% confidence interval will be calculated for each dose group. The two-sided 95% confidence intervals of the differences between the D40 group and O20 group and between the D20 group and O20 group are calculated, and the data will be analysed as in the case of primary variable.

Presence/absence and severity of patient-reported GERD symptom

Since the presence or absence of GERD symptom is not included in the eligibility judgment criteria, not all of the subjects have symptoms at the baseline. Therefore, the subject will be classified and assessed by the presence or absence of symptom at the baseline.

Sustained absence of each symptom or all symptoms are handled as an event. The time to event (up to the first day of 7 consecutive days free of each GERD symptom or of all GERD symptoms) from the starting day of investigational product administration will be analysed by Kaplan-Meier method and Kaplan-Meier plot of sustained absence (the proportion of subjects without each GERD symptom during the 7 days preceding visits at Week 1, 2, 4 and 8) will be for each dose group. The sustained absence-time curves between the D40 group and O20 group, and between the D20 group and O20 group will be compared by Log-rank test. If possible, the median value of the time to event will be obtained in each dose group by Kaplan-Meier method.

The proportion of subjects without each GERD symptom or with ‘Mild’ GERD symptoms up to 1 day during the 7 days preceding visits at Week 1, 2, 4 and 8 and their 95% confidence interval will be calculated for each dose group.

PRO

The descriptive statistics of 5 domain scores of QOLRAD at each assessment point will be obtained for each group.

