4.6.2 Patient-reported symptoms

4.6.2.1 Patient diary

The patient diary () is used to record the presence or absence of GERD symptoms and, if any, the intensity (severity) and frequency of symptoms during the treatment period. The investigator(s) or study coordinator instructs the subject how to complete the patient diary and asks the subject to start the diary from the day of diary distribution (at Visit 2).

The patient diary is distributed to the subjects on the scheduled visit of Visits 2 and 3 and the patient is asked to bring it on the next scheduled visit (Visits 3 and 4). The investigator(s) or study coordinator collects the diary after verifying the completion of diary by the subject as instructed. The collected patient diaries are submitted to the sponsor.

Once a day (preferably at the time of getting up) every day, the subject completes (selects) the replies to the questions about the presence or absence of GERD symptoms and the intensity the day before. However, on the starting day of diary, the subject completes (selects) the replies to the questions about the presence or absence of GERD symptoms during the 7 days before Visit 2, the intensity and frequency for the purpose of baseline symptom assessment.

Questions and replies

Questions:

Presence/absence of GERD symptoms

(Replies on the starting day of diary are for the past 7 days and those on Day 2 onward are for the day before.)

- I A burning feeling, rising from the stomach or lower part of the chest towards the neck?
- II Flow of sour or bitter fluid into mouth?
- III Central upper abdominal pain?
- IV Difficulties in swallowing?

Reply choices (the patient selects one of the following 4 grades):

Intensity of GERD symptom

- 0 No symptom.
- 1 Awareness of symptoms but easily tolerated.
- 2 Discomfort sufficient to cause interference with daily activities (meals, work, sleep, etc.).
- 3 Incapacitating, with inability to perform daily activities (meals, work, sleep, etc.).

Frequency (only on the starting day of diary):

How often did these symptoms occur in the past week?

- a) 0 day
- b) 1 day
- c) 2-3 days

d) 4-6 days

e) 7 days

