6.2.2 Secondary outcome variables

The secondary outcome variables of this study are as follows.

Efficacy

- Presence/absence of RE at Week 4 according to LA classification.
- Time to sustained resolution of each GERD symptom (definition: number of days from the starting day of investigational product administration up to the first day of 7 consecutive days free of that symptom).
- Time to sustained resolution of all GERD symptoms (definition: number of days from the starting day of investigational product administration up to the first day of 7 consecutive days free of all symptoms).
- The proportion of subjects without each GERD symptom during the 7 days preceding visits at Week 1, 2, 4 and 8.
- The proportion of subjects without each GERD symptom or with 'Mild' GERD symptoms up to 1 day during the 7 days preceding visit at Week 1, 2, 4 and 8.
- QOLRAD

Safety

- AEs
- Laboratory test values
- Vital signs (blood pressure and pulse rate)

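### The secondary symptom-resolution comparison classifies subjects only by symptom presence at baseline; stratifying the log-rank tests by the baseline frequency already collected would recover sensitivity at no cost

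*Protocol*

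**What the plan says.** Section 6.2.2 defines time to sustained resolution of each symptom as "number of days from the starting day of investigational product administration up to the first day of 7 consecutive days free of that symptom", with a matching definition for all symptoms together.

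Section 6.4.2.1 notes that symptoms are not an entry criterion, so "not all of the subjects have symptoms at the baseline". It draws the consequence: "Therefore, the subject will be classified and assessed by the presence or absence of symptom at the baseline". No threshold for presence is given. The event time runs "up to the first day of 7 consecutive days free of each GERD symptom or of all GERD symptoms". Kaplan-Meier curves for D40 versus O20 and D20 versus O20 "will be compared by Log-rank test", with no stratum or covariate named. A second set of proportions counts subjects who are symptom-free or have Mild "GERD symptoms up to 1 day during the 7 days preceding visits at Week 1, 2, 4 and 8".

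Section 4.6.2.1 has the subject report, on the first diary day, "presence or absence of GERD symptoms during the 7 days before Visit 2, the intensity and frequency for the purpose of baseline symptom assessment". Intensity is graded 0 to 3. The frequency question is "How often did these symptoms occur in the past week", answered as 0, 1, 2-3, 4-6 or 7 days. The wording is plural, and the protocol text does not make clear whether frequency is recorded separately for each of the four symptoms.

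**The concern.** The event is a run of 7 symptom-free days. How easily a subject reaches it depends strongly on how often the symptom occurred before treatment. A subject with heartburn on 1 day in the baseline week and a subject with heartburn every day fall in the same class, yet the first can reach the event without any help from the drug.

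Infrequent sufferers therefore contribute many early events in all three arms. This pulls the curves together and makes the medians and resolution rates partly a description of the case mix. The comparator is active, so differences in symptom relief may be small and sensitivity matters. The variable that would sharpen the comparison is already in the diary but has no place in the analysis the protocol describes.

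The Mild criterion has a related weakness that needs no assumption about frequency mix. Taking diary intensity 1 as Mild, a subject with one such day in the baseline week counts as having the symptom, yet already meets the later responder criterion before the first dose.

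**Working it through.** The protocol states no power, event count or expected resolution rate for the symptom endpoints. The 172, 182 and 185 per group in section 6.5 concern healing only. There is no figure on this point to reproduce.

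**Step 1: chance of the event with no drug effect**

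Inputs from the protocol: a 7-day run (6.2.2, 6.4.2.1), diary categories of 1, 2-3, 4-6 and 7 days (4.6.2.1), and follow-up of about 28 days if healed at Week 4, otherwise up to 56 days (3.1). Assumption: days are independent, with daily symptom probability q = d/7 for d symptom days a week.

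Let r = 1 − q and let F(t) be the probability that a 7-day free run has been completed by day t. Then F(t) = 0 for t < 7, F(7) = r⁷, and F(t) = F(t−1) + [1 − F(t−8)]·q·r⁷ for t ≥ 8.

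For d = 1:
- r⁷ = (6/7)⁷ = 0.340, and q·r⁷ = 0.340/7 = 0.0486.
- F(14) = 0.340 + 7 × 0.0486 = 0.680.
- Continuing the recursion, F(28) = 0.935 and F(56) = 0.997.
- F(10) = 0.486 and F(11) = 0.534. The median run ends on day 11 and so starts on day 5.

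| Symptom days per week | Run starts on day 1 | By day 28 | By day 56 |
|---|---|---|---|
| 1 | 34.0% | 93.5% | 99.7% |
| 2 | 9.5% | 56.3% | 83.8% |
| 2.5 | 4.5% | 35.2% | 61.5% |
| 3 | 2.0% | 19.0% | 37.3% |
| 4 | 0.3% | 3.4% | 7.5% |
| 5 | about 0 | 0.2% | 0.6% |
| 6-7 | about 0 | about 0 | about 0 |

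If symptom days cluster (lag-1 correlation 0.2 to 0.4), the day-28 figures become 96-98% at 1 day, 52-68% at 2.5 days and 2-10% at 5 days. The gradient across frequencies remains.

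**Step 2: what stratifying gains**

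None of these inputs is in the protocol; all are assumed:
- 150 symptomatic subjects per arm, 28 days of follow-up.
- Baseline daily symptom probabilities of 1/7, 2.5/7, 5/7 and 0.98 in the four frequency classes.
- Daily risk on treatment cut to 30% of baseline in one arm and 38% in the other.
- Two-sided 5% log-rank test. The stratified statistic is (ΣU)²/ΣV, summed over frequency classes.

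| Assumed mix (1 / 2-3 / 4-6 / 7 days) | Unstratified → stratified power | Repeat with 4,000 trials |
|---|---|---|
| 25/30/30/15% | 58% → 73% | 59% → 70% |
| 15/25/35/25% | 72% → 84% | 71% → 81% |
| 5/15/40/40% | 85% → 93% | 85% → 91% |

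The gain is roughly 8 to 15 points in the first set and 6 to 12 in the larger one. In the larger set, merging to two strata (1-3 versus 4-7 days) gave 68%, 79% and 89%, so the coarser split keeps much of the gain. With equal arms, both tests rejected in about 5% of trials.

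**The case against.** The strongest reply is that nothing here is an error. An unstratified log-rank test among symptomatic subjects is a valid test. Section 6.1 announces a comprehensive statistical analysis plan before unblinding, and strata for a secondary test are ordinary content for it. The endpoints are secondary, carry no promised power and decide nothing about non-inferiority. All the power figures rest on inputs the protocol does not give.

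Most of this stands and sets the severity. It does not remove the point. The protocol does not leave the classification open: it gives a rule and a test. For healing, section 6.4.1 names strata (LA grade or CYP2C19 genotype); for symptoms it names presence or absence alone. A better analysis is available from data already collected.

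A reader might infer more than the document supports:
- **That the comparison is biased or the type I error inflated.** It is not. Chance resolution acts alike in all randomised, blinded arms, and the simulated error rate is nominal.
- **That randomising only by LA grade is a defect here.** Chance imbalance in an unstratified factor is already covered by the nominal error rate.
- **That the protocol defines presence as at least 1 day in 7.** It gives no threshold. That reading follows from the diary scale only.
- **That frequency and intensity will go unused.** The protocol names no analysis role for them; the analysis plan is not available and may give one.

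**Conclusion.** The point holds as an avoidable loss of sensitivity in secondary endpoints. Presence alone pools subjects whose chance of the event without drug effect ranges from about 93% (1 day a week) to almost nil (5 or more days) within 28 days, if days are independent. Pooled medians and proportions will therefore depend on the frequency mix.

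The size of the loss is unknown. The power gains depend on the assumed mix, effect and number of symptomatic subjects, and shrink when few subjects have infrequent symptoms. The primary healing analysis, the non-inferiority conclusions and the sample size are untouched. Severity is low.

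**What to change.** Before unblinding, in section 6.4.2.1 or the statistical analysis plan:

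- State what counts as presence of a symptom at baseline.
- Among subjects with the symptom at baseline, stratify the D40-O20 and D20-O20 log-rank tests by the diary's baseline frequency category (1, 2-3, 4-6, 7 days). Use the symptom's own frequency if it is recorded per symptom, otherwise the single frequency reported.
- Give a rule for merging sparse categories, for example 1-3 versus 4-7 days for the rarer symptoms.
- Show Kaplan-Meier curves and the visit proportions for 1-3 versus 4-7 days alongside the pooled results.

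The cost is a few lines of text and some extra tables and figures. The data are already collected, so there is no added burden for patients or sites.

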If a Randomisation code is assigned incorrectly, no attempt should be made to remedy the error once investigational products were dispensed. The subject will continue with the allocated randomised code and investigational products. AstraZeneca KK should be notified as soon as the error is discovered. Randomisation of subsequent subjects will continue using the first unallocated Randomisation code in the original sequence.

The investigational product given to individual subjects will be determined by a randomisation schedule. The details of the treatment allocations are described in “Procedures for drug accountability”.

At least 100 patients with grade C or D RE according to LA classification will be enrolled. If 455 subjects with grade A/B according to LA classification are allocated, no more subject

with grade A/B according to LA classification will be allocated except for the subject who have already start the screening test.

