6. STATISTICAL METHODS AND DETERMINATION OF SAMPLE SIZE

6.1 Statistical evaluation – general aspects

A comprehensive Statistical Analysis Plan will be prepared before unblinding of the data. A significant level of $p < 0.05$ (two-sided) will be used, in principle, for statistical tests and interval estimation.

All statistical analyses in this study will be performed by Statistics and Programming Department of AstraZeneca KK using the SAS software.

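### The log-rank tests of time to sustained symptom resolution name no strata, although randomisation is stratified by LA grade. Naming the strata is a minor, nearly free improvement.

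*Protocol*

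**What the plan says.** Protocol section 3.5: "Subjects will be classified based on the LA classification in grade A/B and C/D, and randomised to one of the D20, D40 or O20" groups, 1:1:1 within each grade class. The same section sets the size of the smaller class, "At least 100 patients with grade C or D RE according to LA classification will be enrolled", and closes grade A/B at 455 allocated subjects, apart from those already in screening.

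Section 6.4.1 compares Week 8 healing "using Cochran-Mantel-Haenszel test stratified by baseline LA classification or CYP2C19 genotype". Section 6.4.2.1 analyses Week 4 healing in the same way as the primary variable.

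Later in section 6.4.2.1, time to sustained resolution (of each symptom and of all symptoms) is analysed by Kaplan-Meier. The curves for D40 and O20 and "between the D20 group and O20 group will be compared by Log-rank test". No strata are named. The only subdivision given is that "the subject will be classified and assessed by the presence or absence of symptom at the baseline".

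Section 6.1 sets a two-sided 5% level in principle and promises a statistical analysis plan before unblinding.

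**The concern.** LA grade was judged important enough to stratify the randomisation and is offered as a stratifier for the healing test, yet it does not appear in the symptom tests. Balancing the arms on a prognostic factor reduces the true variability of the log-rank score. The plain test does not credit that reduction, so its statistic varies less than its standard error implies. Pooling strata with different event rates also dilutes the treatment contrast over follow-up.

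Among the symptom and quality-of-life outcomes, time to sustained resolution is the only one with a planned between-arm test. The symptom proportions get confidence intervals per group, and QOLRAD gets descriptive statistics. What is at stake is the sensitivity of the one formal comparison behind the secondary symptom objective.

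**Working it through.** **The protocol's own figures.** Section 6.5 gives no power, event count or hazard ratio for the log-rank tests. Its sample size concerns healing only, and it reproduces: n = (1.960 + 1.282)² × (0.82×0.18 + 0.85×0.15) / (0.03 + 0.10)² = 10.51 × 0.2751 / 0.0169 ≈ 171.04, rounded up to 172 per group. The trial randomises 185 per group.

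**Stratum sizes.** 100/555 = 18.0% grade C/D. Per arm, 185 × 100/555 ≈ 33 are C/D and 185 − 33 = 152 are A/B. Since A/B is capped at 455 (455/555 = 82.0%), 18% is roughly the lower end of the C/D share.

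**Observation window.** A symptom-free run of 7 days within 56 days must start by day 56 − 6 = 50.

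**Test statistics.** At each event day j, with d events (d₁ in the test arm) among n at risk (n₁ in the test arm):

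- U = Σ (d₁ − d·n₁/n)
- V = Σ d·(n₁/n)(1 − n₁/n)(n − d)/(n − 1)
- Plain test: Z = U/√V over all subjects.
- Stratified test: Z = (U_AB + U_CD)/√(V_AB + V_CD).

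**Assumptions not in the protocol.** Exponential times with a median of 10 days in A/B; treatment hazard ratio 1.38; all subjects symptomatic at baseline and followed to day 50. The C/D-to-A/B hazard ratio for resolution is unknown and is varied.

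**Result** (8,000 runs per setting, 18% C/D, two-sided 5%):

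| C/D vs A/B rate ratio | SD of plain Z under no effect | Plain type I error | Plain power | Stratified power | Loss (points) |
|---|---|---|---|---|---|
| 1.0 | 1.010 | 5.1% | 85.9% | 85.5% | −0.4 |
| 0.8 | 1.006 | 5.2% | 85.5% | 85.5% | 0.0 |
| 0.67 | 0.999 | 4.8% | 84.6% | 85.6% | 1.0 |
| 0.5 | 0.963 | 4.1% | 81.5% | 85.4% | 3.9 |
| 0.33 | 0.910 | 3.3% | 74.8% | 84.7% | 9.9 |

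The simulation standard error is √(0.05×0.95/8000) ≈ 0.24 points for type I error and √(0.85×0.15/8000) ≈ 0.40 points for power. The stratified test's type I error stayed between 5.0% and 5.3%.

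**Cross-check of the conservatism.** If Z has standard deviation s, the true level is 2[1 − Φ(1.96/s)]. For s = 0.963 this is 2[1 − Φ(2.035)] ≈ 4.2%, and for s = 0.910 it is 2[1 − Φ(2.154)] ≈ 3.1%. Both agree with the simulated 4.1% and 3.3%.

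**Sensitivity.**

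- A separate run with 152 and 33 per arm and the same follow-up gave losses of about 1, 4 and 12 points at 0.67, 0.5 and 0.33.
- With 35% C/D, the losses at 0.8, 0.67, 0.5 and 0.33 are 85.4 − 85.3 = 0.1, 85.9 − 84.1 = 1.8, 84.8 − 79.5 = 5.3 and 82.4 − 68.7 = 13.7 points.
- When grade is not prognostic, stratifying costs at most about 1.5 points, near simulation error, even in subsets of 30 A/B and 7 C/D per arm.

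**The case against.** The strongest reply is that nothing here is stated wrongly. The protocol does not call the test unstratified, and strata for a secondary test are often settled in the analysis plan, which is not shown. That stands as far as it goes: a reader might infer that the sponsor decided against stratifying, or that the protocol contradicts itself, but silence supports neither. What remains is that the protocol does name strata for healing, and in the same section names a symptom test without them. As written, the method reads as an ordinary log-rank test.

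A reader might also infer that the planned tests are in fact conservative and underpowered. The documents do not support this. Section 3.2.1 reports overseas healing results by LA grade, but nothing links grade to symptom resolution. At rate ratios of 0.8 to 1.0 there is no detectable difference, and a material loss needs a ratio of about 0.5 or lower.

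Three further points stand:

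- Numbers per symptom will be below 185 per arm, because not every subject has each symptom at baseline. With about 33 C/D subjects per arm before that split, the C/D stratum is not large.
- Subjects healed at Week 4 leave the study then, so actual follow-up is a mixture. The day-50 figures do not represent early leavers.
- The plain test corresponds to the unstratified Kaplan-Meier curves planned for each dose group, which is a coherent choice. Those plots can stay as they are if the test is stratified.

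**Conclusion.** The point holds as a minor improvement and is not an error. The plain log-rank test is valid: no setting showed type I error above 5% beyond simulation error, so any reading that the symptom tests are invalid or anti-conservative is unsupported. The possible cost is lost power, conditional on how strongly LA grade predicts symptom resolution. With 18% C/D and follow-up to about day 50, it is about 0 to 1 point at a rate ratio of 0.67 to 1.0, about 4 points at 0.5 and about 10 to 12 points at 0.33. The corresponding plain type I error is about 5%, 4.1% and 3.3%. These sizes rest on assumed resolution times, an assumed treatment effect and full symptomatic arms, none of which the protocol gives. The comparisons are secondary with no stated power target. The Week 8 non-inferiority conclusion and the sample size are untouched.

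**What to change.** In section 6.4.2.1, for both D40 versus O20 and D20 versus O20, specify a log-rank test stratified by baseline LA grade (A/B, C/D). Use the same two classes as the randomisation. If the protocol is not amended, put the same statement in the analysis plan before unblinding.

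The cost is one phrase and one option in the analysis program. No data collection, sample size or primary analysis changes. The statistical price if grade turns out not to be prognostic is at most about 1.5 points of power in small per-symptom subsets.
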